12.8.2.2 Hy's Law

Hepatic function abnormality defined by an increase in AST and/or ALT to $\geq 3 \times$ ULN concurrent with an increase in total bilirubin to $\geq 2 \times$ ULN but without increase in alkaline phosphatase (i.e., alkaline phosphatase $< 2 \times$ ULN) meets the criteria for Hy's law and raises the concern for drug-induced liver injury when no other cause is identified.

The number and percentage of patients meeting Hy's Law at each scheduled visit during the on-treatment period will be summarized.

An eDISH figure displaying patients who reach 3xULN for ALT or AST, plus 2xULN for total bilirubin and thus are at risk for a drug induced liver injury according to Hy's law will be presented for all patients. A listing of patients at risk will also be presented.

12.8.2.3 TSH assessment

Results will be summarized and listed for thyroid parameters: TSH, Free T4, Total T3 and Free T3.

12.8.3 Vital Signs

The following vital signs will be summarized: heart rate (beats/min), systolic blood pressure (SBP; mmHg), diastolic blood pressure (DBP; mmHg), and body temperature (C).

The selected vital signs will be summarized descriptively at each study timepoint where they are collected. CFB values will be summarized for the on-treatment time points. All vital signs will be listed.

The actual values and CFB for each scheduled study visit for selected vital signs parameters will be plotted at each time point up to and including Cycle 10 using a line plot including confidence intervals around the mean.

12.8.4 ECOG Performance Status

A tabulation of ECOG performance status by timepoint will be provided, including the number and percentage of patients reporting each ECOG category at each scheduled time point.

12.8.5 Physical Examinations, ECGs, and Other Observations Related to Safety

Summaries of these safety assessments will be tabulated by indication at each assessment timepoint.

12.8.5.1 Physical Examination

Physical examination data will be listed only.

12.8.5.2 Electrocardiogram

Summaries will be generated for patients based on International Council for Harmonization (ICH) E14 category, with QTcF in categories <450msec, 450-480msec, or increased to value >480 and ≤500 msec, and value >500 msec, and patients with CFB in QTcF increased by ≤30 msec, >30 to ≤60 msec, and by >60 msec.

The actual values and CFB for each scheduled study visit for selected ECG parameters will be plotted at each time point up to and including cycle 10 using a box-whisker plot including an overlaid mean profile line.

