43	Specification of study population in response to the French National Agency for the Safety of Medicines and Health Products (ANSM)'s request	
Revised in response to ANSM's request (ANSM 22Apr2022):
 
To amend inclusion criterion 4 for disease characteristics as following :
 
- NSCLC: add to the description of the advanced
	1.1 Synopsis, 1.2 Schema, 4.2 Scientific rationale for study design, 5.1 Inclusion criteria

Change number	Description of change	Rationale for change	Section(s) in Protocol Amendment 1
		
setting “not amenable to curative treatment” and change “and/or” by “and” for immune checkpoint inhibitor and platinum containing regimen
 
- cSCC : mention that inclusion of patients is possible only in cSCC when association with RT is not feasible
 
In addition the sponsor is requested to further substantiate the rationale for a direct rechallenge with immunotherapy instead of using cytotoxic chemotherapy
 
- mCRPC : make clear that patients should have received abiraterone and enzalutamide
	
44	Addition of management recommendations for cytokine release syndrome, shortening of the QT interval, and injection site reaction	
Revised in response to ANSM’s request (ANSM 22Apr2022):
 
To amend study protocol section 6.5 so as to include description of toxicity management for identified and potential risks of SOT101, especially CRS, shortening of QT and injection site reaction. Indeed, the sole reference of “discussion on a case-by-case basis between the site and the sponsor’s medical monitor” is not considered sufficient. Protocol should include or refers to guidelines for the management of the identified and potential risks for the experimental treatment. Management of increased ALT and AST is adequately described in table 6.2. Considering the risk of CRS, the protocol should include
	6.5.1 Dose modification and toxicity management for nanrilefusp alfa, 6.5.3 Clinical management of cytokine release syndrome

Change number	Description of change	Rationale for change	Section(s) in Protocol Amendment 1
		stopping rules for the experimental product in addition to the reference to guidelines for the management of CRS.	

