### Medical conditions

8. Clinically significant cardiac abnormalities including prior history of any of the following:
  - 8.1. Cardiomyopathy, with left ventricular ejection fraction  $\leq 50\%$  at screening
  - 8.2. Congestive heart failure of New York Heart Association grade  $\geq 2$
  - 8.3. History of clinically significant (i.e., active) atherosclerotic cardiovascular disease, specifically myocardial infarction, unstable angina, cerebrovascular accident within 6 months prior to the first dose of study interventions, and any clinically significant history of coronary heart disease and clinically significant artery disease within the past 5 years
  - 8.4. Prolongation of QTcF  $>450$  msec

---

- 8.5. Clinically significant cardiac arrhythmia that cannot be controlled with adequate medication
- 9. Uncontrolled hypertension defined as systolic blood pressure >160 mmHg, diastolic blood pressure >110 mmHg. Patients with uncontrolled hypertension should be medically managed on a stable regimen to control hypertension prior to study entry (ICF signature).
- 10. Has undergone prior allogeneic hematopoietic stem cell transplantation within the last 5 years. Patients who have had a transplant more than 5 years ago are eligible as long as there are no symptoms of graft versus host disease.
- 11. Has had an allogeneic tissue/solid organ transplant
- 12. Has a diagnosis of immunodeficiency or is receiving chronic systemic steroid therapy (in dosing exceeding 10 mg daily of prednisone equivalent) or any other form of immunosuppressive therapy within 7 days prior to the first dose of study interventions
- 13. History of or serology positive for HIV. A locally performed HIV test is required during screening.
- 14. Has a known additional malignancy that is progressing or has required active treatment within the past 5 years. Patients with basal cell carcinoma of the skin or carcinoma *in situ* excluding carcinoma *in situ* of bladder that have undergone potentially curative therapy are not excluded.

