### **6.5 Dose modification and toxicity management**

#### **6.5.1 Dose modification and toxicity management for nanrilkefusp alfa**

Dose modification and toxicity management for nanrilkefusp alfa for safety reasons will be discussed on a case-by-case basis between the site and the sponsor's medical monitor.

Transient pyrexia is a frequent AE after nanrilkefusp alfa injection. The use of, e.g., ibuprofen, and other non-steroid premedication can be considered according to local standard practice for prevention and treatment of fever.

Recommendations for clinical management of cytokine release syndrome are provided in section [6.5.3](#).

To minimize the risk for injection site reaction, subcutaneous injection sites should be rotated to different areas of the body (upper and lower extremities, each of the 4 quadrants of the abdomen).

To minimize the risks associated with shortening of the QT interval, vital signs and ECG must be closely monitored as per Protocol and institutional guidelines.

Liver function tests for nanrilkefusp alfa toxicity evaluation in this study will include AST, ALT, total bilirubin, and alkaline phosphatase.

Nanrilkefusp alfa-related hepatic toxicities should be managed as shown in [Table 6.2](#).

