### 6.8.2 Prohibited medications

Medications or vaccinations specifically prohibited in the exclusion criteria are not allowed during the ongoing trial. If there is a clinical indication for any medication or vaccination specifically prohibited during the trial, discontinuation from study interventions or vaccination may be required (also see section [7.1](#)). The investigator is to discuss prohibited medication/vaccination with the sponsor's medical monitor. The final decision on any supportive therapy or vaccination rests with the investigator and/or the patient's primary physician. However, the decision to continue the patient on study interventions requires the mutual agreement of the investigator, the sponsor, and the patient.

The following medications and vaccinations are prohibited during the study:

- Concomitant use of drugs known to prolong the QT/QTc interval is prohibited during the study. Some of the medications known to prolong the QT interval are: amiodarone, azithromycin, ciprofloxacin, chlorpromazine, citalopram, domperidone, donepezil, escitalopram, fluconazole, haloperidol, levofloxacin, levomepromazine, methadone, ondansetron, and sulpiride. A complete list of medications known to prolong the QT interval can be found at [www.crediblemeds.org](http://www.crediblemeds.org).

- Antineoplastic systemic chemotherapy or biological therapy
- Immunotherapy not specified in this Protocol
- Chemotherapy not specified in this Protocol
- Investigational agents other than nanrilkefusp alfa and pembrolizumab
- Radiation therapy

Note: Radiation therapy to a symptomatic solitary lesion or to the brain may be allowed at the investigator's discretion. Palliative radiotherapy of, e.g., painful bone metastases not defined as indicator lesions is allowed.

- Live or live attenuated vaccines within 30 days prior to the first dose of study interventions, during treatment with nanrilkefusp alfa and/or pembrolizumab, and within 90 days after the last dose of nanrilkefusp alfa and/or pembrolizumab, whichever is later. Note: Killed vaccines are allowed.

Note: Any licensed COVID-19 vaccine (including for emergency use) in a particular country is allowed in the study as long as they are mRNA vaccines, adenoviral vaccines, or inactivated vaccines. These vaccines will be treated just as any other concomitant therapy.

Investigational vaccines (i.e., those not licensed or approved for emergency use) are not allowed.

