#### **8.2.4      Electrocardiography and left ventricular ejection fraction**

During the study, patients with signs or symptoms of chest pain, murmurs, gallops, irregular rhythm, or palpitations must be further assessed if clinically indicated, including the need for hospitalization. Standard 12-lead ECG will be done locally at the site for assessment of any change in QTcF interval and other parameters.

Left ventricular ejection fraction will be assessed using either echocardiography or multigated acquisition scanning (MUGA). However, the method chosen needs to stay the same throughout the trial.

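### The QTcF categories in SAP 12.8.5.2 count only high values and increases, so they give no patient count of QT shortening, the QT risk Protocol 6.5.1 names for nanrilkefusp alfa

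*SAP*

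**What the plan says.** Protocol 6.5.1, on toxicity management for nanrilkefusp alfa, states: "To minimize the risks associated with shortening of the QT interval, vital signs and ECG must be closely monitored". Protocol 8.2.4 gives the purpose of the 12-lead ECG as "for assessment of any change in QTcF interval and other parameters", which covers both directions. ECG findings are a secondary safety endpoint (Protocol 3, SAP 7.4). SAP 6.1 drops only the exploratory endpoints after the futility analysis, so this endpoint is still to be reported.

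SAP 12.8.5.2 specifies two categorical QTcF summaries based on ICH E14:

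- Absolute value: "with QTcF in categories <450msec, 450-480msec, or increased to value >480 and ≤500 msec, and value >500 msec".
- Change from baseline: "patients with CFB in QTcF increased by" at most 30, more than 30 and up to 60, or more than 60 msec.

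The section adds box-whisker plots of actual values and change from baseline at scheduled visits up to cycle 10, for a selection of ECG parameters that it does not name. It specifies no continuous QTcF table. The next section, 12.8.5.3, does specify observed values and change for LVEF.

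The protocol also addresses prolongation. Exclusion criterion 8.4 bars patients with QTcF above 450 msec, and section 6.8.2 says: "Concomitant use of drugs known to prolong the QT/QTc interval is prohibited during the study".

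**The concern.** The absolute scale has no lower cut-off and the change scale has no category for a decrease. The direction left out is the one Protocol 6.5.1 tells sites to watch. A reader of the categorical ECG tables would see the same picture whether shortening was absent or common, and could take a table full of small or no increases as reassurance on a question it does not address.

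At stake is the descriptive safety account of a named risk. No efficacy result, decision rule or test depends on it.

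**Working it through.** The plan states no figure to reproduce, and no sample size, power or alpha enters. The check applies the SAP 12.8.5.2 cut-offs to example values. The documents give no QTcF data, so **every baseline and on-treatment value below is an assumption** chosen for illustration.

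**Step 1: where eligible patients start.** Exclusion 8.4 removes QTcF above 450 msec. A patient who meets it at screening is already in the lowest absolute category, or at exactly 450 msec. For any fall d > 0 from such a value, 450 − d < 450. Shortening can only keep or put the patient in the lowest category.

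**Step 2: classify.** Change = on-treatment value − baseline. The change wording has two readings: (a) the lowest category takes every change up to +30 msec, including falls; (b) the category takes only true increases, as literally worded.

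| Baseline | On treatment | Change | Absolute category | Change category, reading (a) | Reading (b) |
|---|---|---|---|---|---|
| 410 | 410 | 0 | <450 | ≤30 | none |
| 410 | 380 | −30 | <450 | ≤30 | none |
| 410 | 350 | −60 | <450 | ≤30 | none |
| 410 | 330 | −80 | <450 | ≤30 | none |
| 410 | 300 | −110 | <450 | ≤30 | none |
| 449 | 340 | −109 | <450 | ≤30 | none |
| 410 | 445 | +35 | <450 | >30 to ≤60 | >30 to ≤60 |
| 410 | 475 | +65 | 450-480 | >60 | >60 |
| 410 | 505 | +95 | >500 | >60 | >60 |

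Under either reading, every fall is coded identically to no change. Rises are separated as intended.

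**Step 3: apply mirrored decrease categories (≤30, >30 to ≤60, >60 msec).** The fall of 30 goes to ≤30, the fall of 60 to >30 to ≤60, and the falls of 80, 109 and 110 to >60. The cases that were indistinguishable now separate.

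**Step 4: can other planned outputs supply the count?**

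- Adverse event tables (SAP 12.8.1.1) count patients, but Protocol 8.3.8.1 asks for abnormal findings to be recorded as adverse events only when clinically relevant. A silent shortening may not be recorded.
- Box plots show distributions by scheduled visit, and only if QTcF is among the parameters chosen. They do not count patients who ever crossed a threshold.
- SAP 12.0 gives continuous variables a minimum, and SAP 12.8.5 and Protocol 9.3.3.1 provide generically for ECG summaries. A per-visit minimum would reveal one extreme value but not how many patients had one.
- Listings (SAP 12.0) hold every value but give no pre-specified frequency. SAP 10.7 sends unscheduled visits to listings only, so an ECG prompted by symptoms would not enter the by-visit outputs.

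**The case against.** The strongest reply is that shortening is not hidden. Clinically relevant cases would be counted in the adverse event tables, the box plots cover both directions of change, the general rules allow a continuous summary with a minimum, and all values are listed. This stands. A reader might infer that the reported frequency of shortening is zero by construction, or that the analysis cannot detect it. The documents support neither: the gap is confined to the categorical tables and to a patient count.

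A reader might also infer that QT shortening is an established signal. The documents do not show that. Protocol 6.5.1 speaks of risks. The regulator's request recorded in the amendment summary names "especially CRS, shortening of QT and injection site reaction" under identified and potential risks together, without saying which kind QT shortening is. It is not among the adverse events of special interest in Protocol 8.3.1.3, and the stated reason for reducing ECG assessments was that no significant cardiac toxicity had been seen. It is a monitored risk.

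Nor are the E14 categories aimed at the wrong thing. The protocol guards against prolongation at entry and through prohibited medication, so counting it is appropriate.

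Finally, the gain from extra rows may be limited. Scheduled on-treatment ECGs fall on day 1 of each cycle before nanrilkefusp alfa (Protocol 1.3.1). In a 21-day cycle run to schedule, that is 22 − 9 = 13 days after the previous day 9 dose. If shortening were acute, which the documents do not say, these ECGs could miss it. This is a real limitation on what the rows can show. It does not justify categories that would miss a recorded fall.

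**Conclusion.** The point holds in a limited form. The specified QTcF categories are one-directional and give no patient count of shortening, although Protocol 6.5.1 names that risk and Protocol 8.2.4 calls for assessing any change. For a patient within the entry limit, this is true of a fall of any size and under either reading of the change wording. The conclusion rests on the cut-offs as written; the example values only illustrate it.

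The ambiguity in the change table is a lesser defect of its own: the SAP does not say whether a patient with a decrease is counted with the smallest increases or left out.

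The consequence is moderate. The study is descriptive and single-arm, recruitment has stopped, and no primary result is affected. The change is still worth making before database lock, because the present rule would conceal a named risk in the table where a reader would look for it.

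**What to change.** Amend SAP 12.8.5.2 as follows:

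1. Keep the E14 categories.
2. Add decrease-from-baseline categories that mirror the existing cut-offs (≤30, >30 to ≤60 and >60 msec), and state where a zero change is counted so that the table is exhaustive.
3. Add low absolute QTcF categories. The documents give no cut-off, so the sponsor should pre-specify and justify them.
4. Count the new categories once per patient on the minimum post-baseline value, including unscheduled ECGs. SAP 12.8.2.1 already takes this approach for laboratory data, presenting each patient's on-treatment minimum and maximum with unscheduled visits included. It needs a stated exception to the listings-only rule in SAP 10.7.
5. Name QTcF among the plotted parameters, and add a continuous summary of QTcF and its change that includes the minimum.
6. State beside the table that scheduled on-treatment ECGs are taken on day 1 before dosing, so the counts may miss acute post-dose shortening.

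The cost is a few table rows and one continuous summary from data already collected. No new assessment is needed.

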12.8.5.3 LVEF

LVEF data will be summarized. Observed values and CFB will be presented for each planned visit.

12.8.5.4 Pregnancy Test

Pregnancy testing data will be listed only.

12.8.5.5 Long Term Follow-up

Survival status data will be listed for the ASaT population. Additionally, all subsequent anti-cancer therapy will be summarized and listed.

12.8.5.6 Death Report

Death report data will be summarized for the enrolled population. Primary and secondary causes of death will be summarized using a combination of coded terms (MedDRA coded PT and SOC terms) and the CRF responses. .

12.9 Serum PK Summaries

All PK analyses will be performed using the PK population.

Descriptive statistics (number of patients, mean, geometric mean, 95% CI for the geometric mean,, STD, coefficient of variation [%CV], median, min, and max) will be used to summarize the serum concentrations descriptively by scheduled timepoint and actual dose received. Summaries will be performed by actual dose received, defined as the actual dose received on the day of PK sampling. All concentrations data will be listed by planned dose level and scheduled timepoints, with the actual dose level received at each timepoint presented at record level.

Serum concentrations of SOT101 below the quantifiable limit (BQL) will be set to 0 in the computation of mean concentration values. The following rules apply:

- If there are less than 3 quantifiable values in a data series, only the minimum, maximum and n will be presented. The other summary statistics will be denoted as not calculated (NC).

- If any of the values at a certain timepoint are BLQ, the geometric mean and geometric coefficient of variation (CV) will be denoted as NC.

PK parameters will be calculated as described in the PK Analysis Plan (PKAP). The units of concentration and resulting PK parameters, with amount or concentration in the unit, will be presented as they are received from the analytical laboratory. PK parameters will be summarized descriptively by timepoint and actual dose received, by indication and overall (number of patients, mean, geometric mean, STD, coefficient of variation [%CV], median, min, and max). Line plots of SOT101 concentration including error bars for \pm SD by timepoint and indication will be presented by profile day showing plots for C1D1, C1D9, C2D1 and C2D9. C1D2 pre-dose will be present on the C1D1 figure as the 24h dose.

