### 1.3.5 Nanrilefusp alfa pharmacokinetic sampling

All attempts should be made to collect the samples on time.

Cycle, day	Time point (pre-dose or time after nanrilefusp alfa administration)	12 patients per indication	Rest of the patients
Cycle 1 day 1	Pre-dose to nanrilefusp alfa	X	
	30 min ( $\pm 5$ min)	X	
	1 h ( $\pm 5$ min)	X	
	2 h ( $\pm 15$ min)	X	
	4 h ( $\pm 30$ min)	X	X
	12 h ( $\pm 2$ h) (optional)	X	
Cycle 1 day 2	Pre-dose to nanrilefusp alfa (-2 h [-15 min] to 0 h)	X	X
Cycle 1 day 8	Pre-dose to nanrilefusp alfa (-2 h [-15 min] to 0 h)	X	
Cycle 1 day 9	Pre-dose to nanrilefusp alfa (-2 h [-15 min] to 0 h)	X	
	2 h ( $\pm 15$ min)	X	
	4 h ( $\pm 30$ min)	X	X
Cycle 2 day 1	Pre-dose to nanrilefusp alfa (-2 h [-15 min] to 0 h)	X	
	2 h ( $\pm 15$ min)	X	
	4 h ( $\pm 30$ min)	X	X
Cycle 2 day 9	Pre-dose to nanrilefusp alfa (-2 h [-15 min] to 0 h)	X	
	2 h ( $\pm 15$ min)	X	
	4 h ( $\pm 30$ min)	X	X
Cycle 3 day 1	Pre-dose to nanrilefusp alfa (-2 h [-15 min] to 0 h)	X	
	2 h ( $\pm 15$ min)	X	X

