8.1 Sample Size Considerations

The number of patients per indication to be treated for at least one cycle is based on a Bayesian calculation: for each indication separately, Markov chain Monte Carlo has been used for the sample size determination. Assuming a desired ORR for the number of responses, and a uniform prior distribution between 0 and 1, there will be at least 80% posterior probability to achieve an effect above the minimal ORR:

- Indication 1 (NSCLC): 50 patients
- Indication 2 (MSI-H/dMMR colorectal cancer): 57 patients
- Indication 3 (cSCC): 57 patients
- Indication 4 (advanced hepatocellular carcinoma): 55 patients (not applicable in France)
- Indication 5 (mCRPC): 51 patients
- Indication 6 (recurrent ovarian cancer): 50 patients

This results in a total of 320 patients.

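### SAP 12.9 groups pre-dose PK samples by the dose given later that day, so a trough falls under the wrong dose, or under none, when the dose is changed or withheld

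*SAP*

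**What the plan says.** SAP 12.9 sets the strata for the concentration tables: descriptive statistics "will be used to summarize the serum concentrations descriptively by scheduled timepoint and actual dose received". It then defines the second stratum: "Summaries will be performed by actual dose received, defined as the actual dose received on the day of PK sampling". Nothing in the section treats pre-dose samples differently.

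Protocol 1.3.5 schedules samples labelled "Pre-dose to nanrilefusp alfa (-2 h [-15 min] to 0 h") on C1D2, C1D8, C1D9, C2D1, C2D9 and C3D1. Each is drawn in the two hours or so before that day's injection. The full schedule applies to "12 patients per indication"; the remaining patients give six samples, one of them pre-dose (C1D2).

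Two other rules in SAP 12.9 bear on the point. For the figures, "C1D2 pre-dose will be present on the C1D1 figure as the 24h dose". The rule for the listings begins "All concentrations data will be listed by planned dose level and scheduled timepoints, with the actual dose level received at each timepoint presented at record", so each listed record carries its own actual dose.

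Concentration of nanrilkefusp alfa over time is a secondary endpoint (Protocol 3; SAP 7.4).

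**The concern.** A pre-dose concentration is what remains of earlier injections. The injection given minutes or hours afterwards cannot have contributed to it. A rule keyed to the calendar day of sampling therefore uses the wrong injection for every pre-dose sample after the first dose. While all injections are at the same dose, the wrong injection carries the right label and nothing shows. Once the dose changes or is withheld, the label is wrong or missing.

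The plan anticipates such changes. Protocol 6.5.1 leaves dose modification to case-by-case discussion, and Table 6.2 describes withholding and resuming at 9 µg/kg. SAP 9.5 admits to the efficacy population patients who started cycle 2 without all four cycle 1 injections. SAP 12.8.1.1 plans tables of dose reductions and temporary discontinuations of SOT101.

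At stake are the trough rows of a secondary-endpoint table. A reader would take a trough in a reduced-dose row as evidence about that dose, when it may have been produced by the higher one.

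**Working it through.** The plan gives no figure to reproduce. The check counts the samples exposed and follows the rule through the possible dosing patterns.

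**Step 1: count the timepoints (Protocol 1.3.5, intensive schedule).** C1D1 6 (including the optional 12 h sample), C1D2 1, C1D8 1, C1D9 3, C2D1 3, C2D9 3, C3D1 2. Total 6 + 1 + 1 + 3 + 3 + 3 + 2 = 19. Seven are pre-dose. C1D1 pre-dose has no earlier dose, which leaves 6 exposed: 6/19 = 32%. The other 12 are post-dose, where the same-day dose is the right label.

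**Step 2: identify the injection each pre-dose sample reflects.** Dosing is on days 1, 2, 8 and 9 of 21-day cycles, so in study days 1, 2, 8, 9, 22, 23, 29, 30, 43.

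| Pre-dose sample | Study day | Preceding scheduled injection | Days since |
|---|---|---|---|
| C1D2 | 2 | C1D1 | 1 |
| C1D8 | 8 | C1D2 | 6 |
| C1D9 | 9 | C1D8 | 1 |
| C2D1 | 22 | C1D9 | 13 |
| C2D9 | 30 | C2D8 | 1 |
| C3D1 | 43 | C2D9 | 13 |

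**Step 3: convert to planned samples.** SAP 8.1 gives the planned size: "This results in a total of 320 patients". Six indications × 12 = 72 intensive patients; 320 − 72 = 248 others.

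- All samples: 72 × 19 + 248 × 6 = 1368 + 1488 = 2856.
- Pre-dose after the first dose: 72 × 6 + 248 × 1 = 432 + 248 = 680, or 680/2856 = 24%.
- Post-dose: 72 × 12 + 248 × 5 = 864 + 1240 = 2104.

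These are ceilings, since SAP 6.1 records that recruitment stopped after the August 2023 futility analysis. Five of the six exposed timepoints can have at most 72 patients; only C1D2 is drawn in everyone. The 680 are exposed samples, not mislabelled ones.

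**Step 4: apply the rule to each dosing pattern.**

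| Preceding scheduled injection | Sampling-day injection | Group under SAP 12.9 | Group by last dose given |
|---|---|---|---|
| 12 µg/kg | 12 µg/kg | 12 | 12 (same) |
| 12 µg/kg | 9 µg/kg | 9 | 12 |
| 12 µg/kg | withheld after the draw | none | 12 |
| not given | 12 µg/kg | 12 | dose of an earlier injection, at a longer interval |

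Row 2 can arise without a missed injection. Suppose a patient has 12 µg/kg on C1D9, a hepatic event that resolves within the 13 days to C2D1, and resumption on C2D1 as Table 6.2 describes. The C2D1 pre-dose value reflects 12 µg/kg but is tabulated under 9 µg/kg; the 2 h and 4 h values that day are labelled correctly.

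In row 4 the label may be right, but the value is no longer what its timepoint implies. With day 8 missed, C1D9 pre-dose is 9 − 2 = 7 days after the last injection instead of 1.

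**Step 5: see where the error lands.** In row 2 the 12 µg/kg group loses one valid trough, which matters little in a large group. The 9 µg/kg group gains one wrong trough. It may be a very small group, and every patient reduced on that very day enters it with a value from the higher dose.

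**Step 6: compare with the figure rule.** Plotting C1D2 pre-dose as the 24 h point of C1D1 ties that sample to the preceding injection, the attribution missing from the table rule.

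**The case against.** The other side has a good deal.

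- **Rarity.** There is one planned dose, PK sampling ends at C3D1, and only one reduced level is specified. A label goes wrong only if the dose changes or is withheld within about six weeks. This stands, and the documents do not allow the frequency to be estimated.
- **Existing safeguards.** SAP 9.4 provides for record-level review and flagging of non-evaluable records before database lock. That could catch a missed preceding injection. It does not re-attribute anything, and a valid 12 µg/kg trough drawn before a 9 µg/kg injection is evaluable, so there would be no reason to flag it. The listings and the recorded sampling times (Protocol 8.4) let a reader rebuild the attribution by hand, but the table stays wrong.
- **No decision depends on it.** The analyses are descriptive (SAP 12.0), no comparison of dose levels is planned, PK parameters follow a separate PK Analysis Plan, and population PK is reported separately (Protocol 9.3.5). With fewer than three quantifiable values, only n, minimum and maximum are shown. All of this stands and limits the consequence.
- **The figure rule is no contradiction.** The figures are by timepoint and indication, not by dose, so placing C1D2 pre-dose at 24 h is a time-axis convention. This also stands; the convention fits attribution to the preceding dose but does not formally contradict the table rule.

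A reader might also infer that the grouping produces below-limit values and so wipes out geometric means, because SAP 12.9 adds: "If any of the values at a certain timepoint are BLQ, the geometric mean" and geometric CV are not calculated. The documents do not support that. Grouping a sample under one dose or another does not change its concentration. The rule applies however doses are grouped, and it is coherent with below-limit values being set to 0. Neither the quantitation limit nor the half-life is given, so no below-limit rate can be stated. Another substitution rule would be a choice between conventions, not the correction of an error.

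**Conclusion.** The point holds in a limited form. As written, SAP 12.9 gives a wrong dose label, or none, to pre-dose concentrations in situations the protocol itself provides for. The exposure is six of 19 intensive timepoints and one of six for the remaining patients. Actual mislabelling is confined to patients whose dose is changed or withheld up to C3D1. Their number is unknown, and with no concentrations in the documents the shift in any trough mean cannot be sized.

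It would be too strong to say that PK samples in general are misattributed: most are post-dose and correctly labelled, and the rule governs summaries rather than listings.

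The conclusion rests on reading the day-of-sampling definition literally and on taking the Protocol 1.3.5 schedule as complete, including the optional 12 h sample. The case for changing it is that the rule is wrong in principle, the endpoint is secondary, and the correction is cheap.

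**What to change.** Replace the definition in SAP 12.9 with wording such as:

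> Post-dose samples are summarized by the dose given that day. Pre-dose samples are summarized by the last nanrilkefusp alfa dose actually given before the sample. Nominal dose categories are used. If the scheduled preceding injection was not given, the pre-dose value is listed and flagged and left out of the by-timepoint summary.

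The nominal categories need defining because SAP 10.14 derives the real dose from volume and body weight, which gives a continuous value. They could be the planned 12 µg/kg, the 9 µg/kg level in Table 6.2, and other. This is a tabulation rule only and changes nothing in patient management.

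The cost is a small extra derivation from administration and sampling times already recorded (Protocol 1.3.1 and 8.4), and slightly fewer values in some trough summaries. The exclusion is strictest at C2D1 and C3D1: if only the day 9 injection was missed, the interval grows merely from 13 to 14 days, yet the value is left out. The sponsor may accept that for a simple rule, since the value still appears in the listing.
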